6. NATIVE AMERICAN OR INTERNATIONAL INDIGENOUS POPULATIONS REVIEW

Signature needed only if research takes place in Indian Country or among international Indigenous populations, actively recruits Native Americans or international Indigenous populations for enrollment, and/or requires stratification of Native Americans or international Indigenous populations as one of the statistical analyses or study aims.

- Social and Behavioral Projects: American Indian Studies, [name]**
- Biomedical Procedures: Office of Outreach and Multicultural Affairs, [name]**

I have examined the proposal cited above and advise that further appropriate tribal/Indigenous approval []is []is not necessary.

Signature _____ Date _____ Print Name _____

FORM: Application for Human Research

NUMBER	FORM DATE	PAGE
F200	02/2014	4 of 14

SECTION 2: GENERAL INFORMATION

1. Not including this project submission, how many:
 - a. Human Research studies is the PI involved in as [key personnel](#)? 14
 - b. Active subjects are there in the PI's open Human Research study/ies? 0
 - c. Investigators are involved on the PI's open Human Research studies? 5
 - d. Research coordinators are involved on the PI's open Human Research studies? 1
2. What is the expected length of this project? Two years
3. Retention of study materials before, during, and after completion of the project:
 - a. Where will the original signed consent and PHI Authorization documents be stored (building name and room)? University Main Campus, 8319
 - b. How long will the data/consents be kept after conclusion of the project?

 6 years

 Other: _____
4. If the Human Research project is funded, identify all sponsoring entity/ies): N/A
5. If funding support is from a federal agency (such as a training grant, infrastructure grant, salary support, project grant, etc.), list federal agency and grant number Smith & Nephew
6. Total funding amount **OR** per subject amount: N/A
7. The Principal Investigator hereby affirms that ALL individuals who meet the definition of "investigator" for this project in the current "Policy on Investigator Conflict of Interest in Research" have completed the mandatory Conflict of Interest training (<http://orcr.arizona.edu/coi/training>) and Disclosure of Significant Financial Interests (<https://uavpr.arizona.edu/COI/>). Yes
8. Will this project be registered on ClinicalTrials.gov because ...? Yes No
 - a. the local PI is the sponsor of the clinical trial (including NIH-funded clinical trials where the local PI is the funding recipient OR IND holder);

OR
 - b. The PI has been designated by a sponsor, contractor, grantee, or awardee to register the clinical trial to ClinicalTrials.gov, as the [Responsible Party](#) (responsible for conducting the trial, and has sufficient data rights)

If yes, please check the appropriate box:

- ClinicalTrials.gov "NCT" number for this trial (define):
- Registration pending

FORM: Application for Human Research

NUMBER	FORM DATE	PAGE
F200	02/2014	5 of 14

Clinical trial does not require registration (click above to see what studies qualify)

SECTION 3. PROJECT NARRATIVE

1) Background

Non-healing wounds required to heal by secondary intention affect the healthcare system and the patients in many ways. For the patient, a non-healing wound considerably increases the pain/discomfort associated with the surgical or medical condition. It affects their quality of life and ability to return to normal activities of daily living. It increases their risk of adverse events related to management of the wound. In addition, a non-healing wound significantly increases the overall cost of medical care- related to the need for more frequent clinic visits and hospitalizations, increased length of stays, the need for repeat operative procedures and wound care supplies (1, 4).

Topical negative pressure (TNP) is a frequently used method to promote the healing of surgical and non-surgical wounds (1). It uses suction to drain excess fluid from the wound thereby reducing the risk of seroma formation and the risk of infection by decreasing the bacterial load. It has also been shown to stimulate localized blood flow and tissue growth, partially by removing excess fluid but also via mechanical stimulation of nearby tissue (1, 3). Understanding these methods of action, TNP is used frequently in the health care setting to assist with wound healing. Management with TNP of chronic wounds and wounds at high risk for separation has been evaluated in many studies. For example, current studies have investigated the use of prophylactic TNP on closed surgical incisions, including investigations in traumatic injuries, hip arthroplasty, acetabular fractures, sternotomy wounds, vulvectomy incisions and post hysterectomy in obese women- all with promising results. However there is a relative lack of adequately powered patient-oriented evidence demonstrating TNP as a statistically significant agent for preventing or treating wound healing complications (1).

Presently, only one study has evaluated TNP in the obstetric population, specifically obese women undergoing a cesarean section. A retrospective cohort study was done at the University of Maryland to evaluate the efficacy of TNP in decreasing postoperative wound complications when placed over a clean, closed incision following cesarean section in obese patients. Their study demonstrated that there were no wound complications in the population receiving TNP versus a 10.4% complication rate in the control group receiving the standard postoperative dressing (2). However, their study was underpowered from its small sample size and did not show statistical significance.

Obesity is widely prevalent in the United States. In 2012, the CDC reported that 35.8% of women were obese, this prevalence increases as income decreases and is highest for non-Hispanic black women (2). Cesarean sections are considered clean-contaminated procedures; this alone increases the risk of a post-operative wound infection. Wound complications occur in 2.5-16% of cesarean deliveries, influenced by many different factors (5). Obesity is a risk factor that nearly doubles the rate of cesarean section; and the risk of post-operative wound infections in obese women after a cesarean

FORM: Application for Human Research

NUMBER	FORM DATE	PAGE
F200	02/2014	6 of 14

section has been shown to double for every 5 unit increase in BMI above 30 kg/m². Given the prevalence and increasing rate of obesity, and the associated complications particularly with operative procedures, it is important that we re-evaluate how to manage the associated complications and utilize the best possible techniques to decrease maternal morbidity.

Additional co-morbidities increase the risk of wound complications in the setting of cesarean section. These morbidities include maternal diabetes mellitus, history of wound infection or breakdown, chorioamnionitis at the time of cesarean, HIV/AIDS, anticoagulant therapies and autoimmune conditions. These patients may also benefit from innovations in wound management.

This study aims to evaluate the use of TNP over a clean, closed incision following cesarean section in high risk women for preventing complications of wound healing. We hypothesize that using TNP over a clean, closed incision following cesarean section in high risk women will significantly decrease and possibly prevent complications to wound healing. This study will be powered appropriately in order to obtain statistically significant results. We anticipate that by using TNP immediately following the operation we can prevent seroma formation, decrease the bacteria load in the wound and stimulate wound healing all to the effect of minimizing or preventing wound separation/breakdown/necrosis.


2) Lay Summary (approximately 400 words)

We aim to carry out a randomized controlled trial. Patients with a condition that increases their risk of a wound complication will be approached for inclusion in the trial. Each participant agreeing to study inclusion will be randomized to either suture alone or to closure of their skin incision with suture and then with prophylactic placement of a wound vac (PICO). The wound vac will be left in place until the day of discharge. Prior to discharge, the bandage will be removed, the wound inspected and a new bandage will be reapplied to the wound. The patient will remove the bandage and wound vacuum on POD#7 at home. Both items can be discarded in a normal trash receptacle. We will also obtain

FORM: Application for Human Research

NUMBER	FORM DATE	PAGE
F200	02/2014	7 of 14

permission to call the participants for a patient satisfaction questionnaire at 1 week post-op, and possibly 2 and 6 weeks if they have not presented for their post op/partum appointments or the questionnaire could not be obtained at their visit. The wound will be re-assessed at their 2 week and 6 week post-op follow up visits. The patients will be assessed by either the Principal Investigator, Co-investigator and/or Senior Investigator at their post-operative clinic visits. The investigator will ask the patient if they have had any postoperative complications since their surgery and will be asked to detail any complications if they answer yes to this question. They will also be asked to confirm that their wound has completely closed at this time.

3) Setting of the Human Research

Patients being approached for inclusion in this study are those presenting to labor and delivery for delivery care or to B-UMCT for their regularly scheduled clinic visit ([name]).

4) Resources available to conduct the Human Research

The Labor and Delivery unit at the Banner –University Medical Center comprises a triage area, up to 14 laboring rooms and 2 fully operational operating rooms.

There are 16 resident physicians, 2 clinical fellows and multiple OBGYN physicians available for the medical care of pregnant and laboring women. There is also around the clock nursing and anesthesia care available 7 days per week.

The postoperative care delivered to patients is on the 7th floor of the hospital, directly below the Labor and Delivery Unit. The same resident physicians and physicians staff this area.

5) Study Population

Pregnant women with high risk obstetric complications who present to Labor and Delivery at B-UMCT for care at time of delivery and/or to the clinic for a regularly scheduled visit will be potential individuals enrolled in our study.

Sample size calculations predict that with a wound breakdown rate of 20% in high risk patients, approximately 80 patients in each group would be needed to show a complication rate decrease to 5%. We will recruit a total of 200 patients, 100 in the control group and 100 in the study group.

When the women partake in the study device, they will no longer be pregnant as the device will be applied post operatively (after the cesarean section).

FORM: Application for Human Research		
NUMBER	FORM DATE	PAGE
F200	02/2014	8 of 14

6) Recruitment Methods and Consenting Process

Patients will be identified by the investigators during the course of their clinical work or by designated study personnel during pre-screening (see Appendix F). Patients eligible for inclusion in this study will be approached by the Principal investigator, Co-investigator, Senior Investigator, and/or study personnel if they meet the following criteria:

Inclusion criteria:

- 1) Maternal Age 18 or above
- 2) Cesarean delivery
- 3) Maternal condition which increases the risk of wound complication. These conditions include: Obesity (BMI >30), diabetes, HIV/AIDS, chorioamnionitis, rheumatologic disease, history of wound complication, anticoagulant therapy.
- 4) Patient able to read and speak English or Spanish (once the consent form has been approved, a translated Spanish consent will be submitted to the IRB for approval, no Spanish speaking patients will be recruited until approval is received)

Exclusion criteria:

- 1) Minors (<18 years of age)
- 2) Non-cesarean wound (ie tubal ligation wound)
- 3) No high risk maternal condition
- 4) Patient unable to read and speak English or Spanish.
- 5) Prisoners

The PI and co-investigators will already be known to the patient per their clinical care and other non-clinical study staff will introduce themselves appropriately when presenting the research material. Please note: A Banner Employee will approach the subject first to ask them if they wish to learn more about the study, before any recruitment may take place. The consent document (see attached to this submission) will be used as an aid in discussing this research with patients. Though there is not script that the study personnel will read out to the patient, the sections of the consent form will be discussed with this patient before study proceedings are undertaken.

Additionally, patients who undergo a C-section when no study personnel are in the hospital may enroll via phone. Eligible patients who have been identified by a physician on Labor and Delivery will be asked if they would like to hear about the study. Those interested will discuss the study via phone with a member of the study staff on the VOTF using the phone disclosure as a guide. Patients will then be consented to the study in person, including access to PHI, by a member of the study staff before they leave the hospital.

We are requesting a partial PHI for recruitment purposes.

FORM: Application for Human Research		
NUMBER	FORM DATE	PAGE
F200	02/2014	9 of 14

7) Procedures involved in the Human Research

The randomization key will be provided by the department of statistics at the University of Arizona. Envelopes with a 1:1 study allocation (wound vac : no wound vac) will be provided and placed in the Pyxis on labor and delivery. The Pyxis is utilized for two reasons: 1) It is a standard place that the allocations can always be kept and 2) Nursing staff are required to access the Pyxis and an electronic log is kept of when the drawer was opened to retrieve an envelope with study allocation. This will provide adequate concealment of the allocations.

Once consent has been obtained from patients, an envelope containing the study allocation will be retrieved from the Pyxis.

- Non-wound vac patients will undergo wound closure with subcutaneous fat closure with Vicryl in all cases that this is practicable (in extremely thin patients, this may not be possible), followed by subcuticular skin closure also using Vicryl. A compression dressing will then be applied. This dressing is usually removed by the clinician the following day.
- Wound vac patients will undergo wound closure with subcutaneous fat closure with Vicryl in all cases that this is practicable (in extremely thin patients, this may not be possible), followed by subcuticular skin closure also using Vicryl. The wound vac system will then be applied over the closed incision. This vac dressing will then be removed on the day of hospital discharge and replaced with a second bandage and the wound vacuum will be re-activated. The patient will remove both and discard on POD#7. This is per the manufacturer’s guidelines for length of use.
- If the patient fails the wound vac therapy- ie the wound separates and requires traditional wound care (packing, wet to dry dressing, etc), then the PICO system is no longer used as part of their care.

Essentially, the standard of care is to close the cesarean section incision. Different providers use different kinds of sutures (made of different material, and of different sizes) or staples to close the subcutaneous fat and the skin. Essentially what we are saying is that all patients in this study would have the subcutaneous fat and skin closed in the same manner (with Vicryl suture). To participate in the trial patients would have to agree to these closure materials - some patients would opt out of the study if they particularly wanted to have their skin closed with staples, for example (though I think that this would be rare as patients tend to prefer suture - it dissolves and does not have to be removed). We chose a standard closure with suture as there is evidence suggesting a lower rate of wound complications with suture as compared to staples.

We thought it would be unrealistic to try to standardize the entire operative approach (closure of the uterus, closure of the fascia) as the different providers working at the hospital may choose not to participate if the approach specified deviated too much from their usual technique.

FORM: Application for Human Research

NUMBER	FORM DATE	PAGE
F200	02/2014	10 of 14

8) Risks to subjects

The risks to subjects are minimal. All wounds will be closed in a way considered evidence-based. The only difference is the wound dressing applied over the closed wound and the time of removal. Though it is possible that the vac remaining over the wound may delay diagnosis of a wound complication this is very unlikely as the dressing is small, and a wound complication without significant surrounding erythema is uncommon.

There is a small risk of loss of protected health information. The PI will mitigate this risk by keeping all consents in a locked cabinet and not keeping any patient identifiers with the data analysis documents.

9) Potential benefits to subjects and/or society

Patients will receive no monetary benefit from being in this study.

If the hypothesis of this study is correct, those in the treatment arm (ie the wound vac arm) may experience a lower rate of wound complications.

Wound management is a common clinical problem encountered in obstetrics. Implications of a lower complication rate with the utilization of wound vacs would include offering this treatment in high risk groups in the future.

10) Provisions to protect the privacy of subjects and the confidentiality of data

Privacy of subjects will be respected at all times during the study. Patients will only be consented in a private area (pre-operative area, clinic room or laboring room). Patients are asked during all encounters with a physician whether or not they would like their family or friends present. Patients will not be required to have support people leave the room for inclusion in the study.

Patient confidentiality will be respected at all times. The records review required for the study will only be performed by those personnel appearing on the VOTF. All documents with traceable patient data (ie consent forms/data collection forms) will be stored in a locked cabinet in the fellow’s office (Room 8327 G). These records will be stored for a period of 6 years.

A data sheet will be created to include all data pertaining to the study without any patient identifiers. This document will be kept separate from the consent forms and data collection forms.

Additionally, a REDCap database will be used to facilitate tracking patient follow-up and statistical analysis when study procedures are completed. The REDCap database will store identifiable information. The REDCap data base will be maintained for 6 years after completion of the study.

11) Access to Private Information

a. Authorization for Access to Protected Health Information

FORM: Application for Human Research

NUMBER	FORM DATE	PAGE
F200	02/2014	11 of 14

Patients agreeing to participate in this study will be made aware that record review of their protected health information will occur as a part of the study. The consent form includes a HIPPA consent.

b. Authorization for Access to Educational Information

N/A

12) Cost to subjects

Patients will not be charged for use of the wound vac. They will otherwise be billed for their hospital care.

13) Subject compensation

Subjects will not be compensated for participation in this study.

14) Medical care and compensation for injury

This study includes no more than minimal risk to subjects. If a patient has a complication during their hospitalization, their insurance will be billed for their care.

15) Monitoring the data for subject safety

N/A as this research poses no more than minimal risk to subjects.

16) Withdrawal of subjects

Patients may withdraw from this research at any time. If withdrawal occurs before vac placement, no additional interaction with an investigator will be needed. If withdrawal occurs after the vac has been placed, the physician caring for the patient will remove the vac as soon as practicably possible.

17) Sharing of results with subjects

Patients will not be contacted regarding the outcome of this research. If the outcomes are published at a later date, subjects will have access to overall results through this medium.

18) Information management

Information management will be the sole responsibility of the investigators. This will be carried out at the University of Arizona. The sponsoring company makes no stipulations regarding publication.

FORM: Application for Human Research

NUMBER	FORM DATE	PAGE
F200	02/2014	12 of 14

19) Drugs, Devices, and Gases

The wound vac (PICO system) is an FDA approved device for wound care. This is not an FDA trial.

20) Multi-site Human Research'

N/A

SECTION 4: LIST OF ATTACHMENTS FOR THIS SUBMISSION

Document Name	Version Date
1. Consent form	1. 8/22/16
2. Data Collection Form	2.
3. Research Protocol	3.
4. Appendix F	4. 8/22/16
5. Patient Satisfaction Questionnaire (for telephone interview)	5.
6. PICO patient information (Smith and Nephew brochure)- PDF	6.

Submission List for F200: Application for Human Research

Required items for all F200 submissions:

- F107: Verification of Training Form
- Current PI/Co-PI CVs or biosketch, if not included with copy of grant application

Other Items as applicable:

- **Biosafety Review letter** (for UA - Institutional Biosafety Committee)
- **Certificate of Confidentiality**
- **Compressed Gases Review letter** (for UA – Research Instrumentation)
- **Contract** – complete or draft copy of contract including budget
- **Data Collection Tools** – surveys, questionnaires, diaries not included in the protocol, data abstraction form for records review
- **Data Monitoring Charter and Plan**
- **Drug/Device information** – Investigator's Brochure, drug product sheet, device manual, user's manual, instructions for use, package insert, IND/IDE documentation, FDA 1572 form, 510k indication, FDA exemption, sponsor determination of device risk, etc.
- **Export Control Review**
- **Grant Application(s)** – complete copy of grant, regardless of home institution or funding agency, and a copy of the Notice of Grant Award

FORM: Application for Human Research

NUMBER	FORM DATE	PAGE
F200	02/2014	13 of 14

- **Informed Consent/Permission/Assent Form(s)** – including study specific release of information documents, DHHS approved sample consent forms. If consent will not be documented in writing, a script of information to be provided orally to subjects
- Other Approval letters (e.g., school districts, Tribal, other IRB approvals)
- **Participant Materials** – All written materials to be provided to or meant to be seen or heard by subjects (e.g. study newsletter, physician to participant letter, wallet cards, incentive items, holiday/birthday cards, certificates, instructional videos/written guides, calendars, certification of achievement, etc.)
- **PHI Authorization Form(s)**
- **Protocol** – including all amendments/revisions, sub- or extension-studies
- **Radiation Safety Review** letter
- **Recruitment Materials** – telephone scripts, flyers, brochures, websites, email texts, radio/television spots, newspaper advertisements, press releases, etc.
- **Scientific Review Committee** letter (for cancer related projects – AZCC SRC; other units as applicable if the unit has a scientific review committee)
- **Site Authorizations** for research purposes and/or access to administrative records/samples
 - External sites (such as schools, other hospitals or campuses, etc.)
 - UAHN University Campus, South Campus and clinics Site Review Authority (SRA) approval
- **Supplemental site information** (for sites engaged in research where the UA is the IRB of record)
 - Copy of any approvals granted from that site (including determinations if this site has an IRB of its own)
 - Site-specific F107
 - Copy of the site's human subjects training policy
 - CV and medical license (if applicable) of site PI
- **Travel Authorization documentation** (for UA – Office of Global Initiatives)
- **Use of retrospective research samples and/or data** – IRB approval letter, original consent under which samples/data were collected, letter allowing access to samples

Submitting documents to the IRB

All materials must be typed and submitted electronically. Maintain electronic copies of all information submitted to the HSPP office in case revisions are required. It is recommended that version dates be used while naming documents.

1. Documents must be submitted to the [contact] account and not to individual staff email accounts. After contact by a staff member future correspondence may be communicated directly to the staff member concerning the submission.
2. **If acknowledgement of receipt is needed, please request a "Read Receipt" through your email server.** If you use Microsoft Outlook 2007, this is accomplished by clicking "Options" and choosing the "Request a Read Receipt" checkbox in a new email.

FORM: Application for Human Research

NUMBER	FORM DATE	PAGE
F200	02/2014	14 of 14

3. One submission request per email (e.g. one new project submission, one continuing review plus attachments, or one modification request).
4. All submissions must have signatures. An email acknowledgement in place of a signature will not be acceptable. If electronic signatures are not available for use, the signature pages may be signed and scanned as a separate Adobe PDF document and attached to the submission email.
5. **Microsoft Word documents are REQUIRED** for (applications, consents, recruitment materials, and data collection instruments (if available)). PDFs may be submitted for documents that typically are not revised by the IRB (e.g. Investigator Brochures, sponsor protocols).
6. The email subject line must include: IRB # (if assigned one), PI Last Name, and type of submission (Modification, New Project, Continuing Review, Reportable Item, etc.).
7. The email must provide a list of the documents submitted for review. While the documents attached do not have to adhere to a specific naming scheme, it is requested that each document be named to clearly reflect what is inside.

Submissions not following these guidelines will be returned without review

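### The 2- and 6-week wound assessment is assigned to the trial's own investigators with no masking to arm in the document shown, although a masked examination looks possible for at least some patients

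*Protocol*

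**What the plan says.** - **Who assesses.** Protocol Section 3, item 2 (Lay Summary), on the 2- and 6-week follow-up: "The patients will be assessed by either the Principal Investigator, Co-investigator and/or Senior Investigator at their post-operative clinic visits". At the same visit, "The investigator will ask the patient if they have had any postoperative complications since their surgery", and she is asked to confirm that the wound has closed. The satisfaction questionnaire may also be taken at these visits.
- **Who the assessors are.** Under item 6 the same investigator roles approach patients for enrolment, and the Principal Investigator and co-investigators are described as known to the patient through her care. Item 4 says of the postoperative floor, compared with Labor and Delivery: "The same resident physicians and physicians staff this area".
- **Safeguard stated.** Item 7 describes envelopes held in the Pyxis and concludes: "This will provide adequate concealment of the allocations". The document shown says nothing on masking the outcome assessment.
- **State of the wound at the visit.** Item 2: "The patient will remove the bandage and wound vacuum on POD#7 at home". Item 7 has subcutaneous fat and skin closed with Vicryl in both arms, and item 8 names the dressing and its removal time as the only difference.
- **Outcome.** Item 1 evaluates the device "for preventing complications of wound healing", while item 5 sizes the trial "with a wound breakdown rate of 20% in high risk patients", falling to 5%, with 100 patients per group.

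**The concern.** Allocation concealment protects the assignment and ends when the envelope is opened. It does not affect how a wound is scored two or six weeks later. As written, the plan gives that scoring to people who enrol the patients, may have looked after them, and have stated the hypothesis that the device reduces complications. Nothing in the text keeps the arm from them.

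The planned comparison is about 20 events per 100 against about 5 per 100, so a few wounds scored differently by arm can matter. Depending on direction, this could produce an apparent benefit or hide a real one. Who examines the wound, and what that person knows, is a matter of trial conduct, and no later analysis can repair it.

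**Working it through.** **1. Can the wound be examined without revealing the arm?** The device comes off on POD 7 and the first scheduled visit is at 2 weeks, so no device is in place. The control dressing is usually off the day after surgery (item 7). Fat and skin closure is the same in both arms. The wound therefore need not reveal the arm at either visit. The arm can still become known through the examiner's own earlier care of the patient, the chart or visit form, the complication interview, or the questionnaire.

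**2. The plan's own figure.** Item 5 gives about 80 per group for 20% against 5%. Alpha, sidedness and power are not stated, so I assume two-sided 5% and 80% power. With mean rate 0.125:

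n = [1.960·√(2·0.125·0.875) + 0.842·√(0.20·0.80 + 0.05·0.95)]² / 0.15² = (0.917 + 0.383)² / 0.0225 ≈ 75.1, so 76 per group (88 with continuity correction).

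At 80 per group, Fisher power is 79.3% and pooled z-test power is 82.5%. The stated figure is consistent with those assumptions, and the masking point does not depend on it. At 100 per group, power is 90.0% (pooled z) or 88.3% (Fisher). Masking changes none of these figures.

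**3. What arm-aware scoring could do (illustration).** Inputs from the Protocol are 100 per group and the 20% rate. The assumption is no true effect, so 20% in both arms, with a share m of all vac-arm events not recorded. The recorded vac-arm rate is then 0.20·(1 − m). The rejection probability is the double binomial sum

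Σᵢ Σⱼ Bin(i; 100, 0.20) · Bin(j; 100, 0.20(1 − m)) · 1{p(i, j) ≤ 0.05},

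with chi-square uncorrected.

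| m (assumed) | Recorded rates | Chi-square | of which favouring vac | Fisher |
|---|---|---|---|---|
| 0 | 20% v 20% | 5.1% | 2.6% | 3.3% |
| 5% | 20% v 19% | 5.5% | 3.8% | 3.6% |
| 10% | 20% v 18% | 6.7% | 5.6% | 4.4% |
| 20% | 20% v 16% | 11.6% | 11.2% | 8.3% |
| 30% | 20% v 14% | 20.7% | 20.6% | 15.8% |

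With 20 expected vac-arm events (0.20 × 100), 10% is 2 events and 20% is 4 events.

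**4. Scaling to what masking can protect.** A masked visit examination affects only events decided at that examination. If a share e of events is decided there and a share s of those is missed, then m = e·s. With e = 0.5 (assumed) and s = 0.20, m = 0.10, which is the 6.7% (Fisher 4.4%) row. To reach the 20% row with e = 0.5, s would have to be 0.20/0.5 = 0.40.

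**The case against.** **Silence is not a statement.** The key sentence comes from a lay summary in an ethics application. Section 4 lists a separate Research Protocol and a Data Collection Form that are not shown, and either could provide masking. This stands as a limit. A reader might infer that the assessors are known to be unmasked, or that the result will be biased, but the document supports neither. It supports only that this text names the assessors and gives no masking.

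**An unaware assessor may not exist for every patient.** The investigators recruit and may treat, the same physicians cover both floors, and the number of listed investigators is not given in the text shown. This also stands. Common closure and removal on POD 7 show that the wound can be examined without revealing the arm, not that an unaware examiner is always available.

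**Part of the outcome is overt.** Item 1 speaks of separation, breakdown and necrosis, and item 7 of a separated wound needing packing. Such events tend to be charted, and the records review in item 10 may recover them. That lowers the stake but does not correct scoring at the visit, and the text does not settle how much judgement the outcome involves.

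**An early difference between arms might also be inferred.** Item 2 writes a pre-discharge inspection for the vac arm: "Prior to discharge, the bandage will be removed, the wound inspected and a new bandage will be reapplied to the wound". A reader might conclude that control wounds go unseen in hospital. The document does not support this, because item 7 says a clinician usually removes the control dressing the next day. Nor does anything shown suggest that the records review differs by arm.

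**Conclusion.** The concern holds for this document, as a worthwhile and inexpensive improvement rather than proof of bias. The visit assessment is given to investigators who recruit and may treat the patients, the only stated safeguard is allocation concealment, and a masked examination is possible for at least some patients.

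The size is illustrative. It rests on a two-sided 5% test, 100 per arm, a 20% rate in both arms, and miss shares that have no source in the documents. The effect is small up to about 10% of all vac-arm events and material from about 20%. Because masking protects only events decided at the examination, reading the table as the gain from masking would overstate it. The direction of any bias is also not established, and the table shows only the case that favours the vac. Confidence is medium, mainly because the attachments are not shown.

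**What to change.** State in the Protocol that:

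- where possible, the 2- and 6-week wound examination is done by an already listed investigator who was not involved in that patient's delivery or inpatient wound care and has not seen her allocation;
- the examiner completes a fixed wound checklist before the complication interview and before the satisfaction questionnaire;
- allocation does not appear on the visit form, and the patient is asked not to mention her dressing;
- any unmasking of the examiner is recorded.

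If the separate Research Protocol already provides this, one sentence here pointing to it is enough.

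The cost is wording, a checklist and scheduling, with no new visit, no new staff and no change to the sample size. The downside is a rota constraint, because the same physicians staff both floors, hence the words where possible. Events before POD 7, patient-reported events and charted events remain unmasked, so bias is reduced and not removed.
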